3.3.1 Eligibility

3.3.1.1 Inclusion Criteria

To be considered for entry into the study, the candidate must meet all of the following criteria:

- 1. Is of legal age (at least 18) on the date the Informed Consent Form (ICF) is signed and has the capacity to provide voluntary informed consent
- 2. Is able to read, understand, and provide written informed consent on the Institutional Review Board (IRB) approved ICF and provide authorization as appropriate for local privacy regulations
- 3. Is a habitual wearer (at least 3 months) of one of the lens types presented in Table 2
- 4. Has typically cleaned and disinfected their pre-study contact lenses daily
- 5. Must have spectacle correctable distance visual acuity through spherocylindrical refraction to 40 letters [0.14 logarithm of the minimal angle of resolution (logMAR)] or better in each eye at 2 meters distance using a high contrast chart
- 6. Has clear central corneas and is free of any anterior segment disorders
- 7. Is a habitual user of a lens care product for cleaning, disinfecting, and storage of lenses
- 8. Requires lens correction in both eyes
- 9. Wears the same brand of contact lens in both eyes
- 10. Agrees to wear study lenses on a daily wear basis for approximately three months
- 11. Is willing and able to comply with all treatment and follow-up study procedures.

3.3.1.2 **Exclusion Criteria**

The candidate is ineligible for entry into the study if they meet \underline{any} of the following criteria:

- 1. Is currently using a hydrogen-peroxide cleaning and disinfecting solution
- 2. Participated in any drug or device clinical investigation within 30 days prior to entry into this study

- 3. Is a female of childbearing potential (those who are not surgically sterilized or postmenopausal) if they meet any one of the following conditions:
 - they are currently pregnant
 - they plan to become pregnant during the study
 - they are breastfeeding
- 4. Has worn gas permeable (GP) lenses within the last 30 days
- 5. Has worn polymethylmethacrylate (PMMA) lenses within the last three months
- 6. Has typically worn their pre-study contact lenses on an extended wear basis, sleeping in their lenses one night or more per week, during the last year
- 7. Has any systemic disease currently affecting ocular health or which in the Investigator's opinion may have an effect on ocular health during the course of the study

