3.3.3 Subject Discontinuation

A subject MAY be discontinued (at the discretion of the Investigator, the Sponsor, and/or the IRB) prior to the final study visit for a variety of reasons, including, but not limited to:

- An AE occurring during the course of the study, which precludes continued treatment or follow-up
- Persistent grade 3 or 4 slit-lamp findings
- Persistent study related symptoms/complaints
- Unacceptable distance lens visual acuity (VA)
- Unacceptable lens centration
- Unacceptable lens movement
- Failure to follow study procedures

A subject MUST be discontinued prior to the final study visit for any of the following reasons:

- Voluntary withdrawal
- Death
- Investigator decision that it is not in the best medical interest of the subject to continue participation in the investigation
- Lost to follow-up (refer to Section 3.3.4)
- Either eye is discontinued
- Becomes pregnant during the study

Prior to discontinuing a subject, every effort should be made to contact the subject, schedule a final study visit, obtain as much follow-up data as possible, and to retrieve all study materials. Adverse events will be followed as described in Section 7.0.

Subject discontinuations must be documented clearly on the source document and applicable eCRF. The Investigator should indicate the PRIMARY (one) reason that the subject was discontinued for each eye. Subjects who voluntarily withdraw from the study are not required to provide a reason for their decision but should be encouraged to share

this information. Subjects that are discontinued from the study following randomization will not be replaced.

Exit Visit assessments should be completed for early discontinued subjects, if possible.

At the final study visit, all study subjects who are discontinuing should be examined to ensure that their ocular health is consistent with pre-study, baseline conditions. Any adverse effects determined to have been reasonably caused by participation in the study will be followed per the standard of care. Participation in the study will not impact poststudy choices of study subjects for correcting their vision using marketed products (e.g., contact lenses and contact lens care solutions).

Whether a subject completes or is discontinued from the study, they will be directed by the Investigator to resume their habitual lens care regimen.

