### 1.2.2. Randomization

An unmasked statistician who is not otherwise involved in the trial will create the randomization schedule.

Each subject will be randomized to one of the treatment arms in a 1:1 ratio (Test to Control). Randomization will be managed using a RTSM system. The randomization will be stratified by lens group and investigational site.

Efforts will be made to enroll subjects in at least three of the lens strata within each site to minimize confounding between site and lens group. While the target enrollment for each lens group is approximately 68 subjects, some lens strata may be difficult to enroll.

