### 3. Study Populations

For the purposes of analysis, the following analysis sets are defined. For eye level analyses, a subject being included in a study population means both of their eyes will be included in the analysis.

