## 4. Statistical Analyses

### 4.1. General Considerations

EMB Statistical Solutions, LLC will generate the statistical analyses, including the associated datasets, detailed in this SAP. Programming for the creation of the datasets and for performing the statistical analyses will be performed using SAS® software, Version 9.4 or later, unless otherwise specified. Programs will be validated as stated in the Quality Control plan prior to finalization. In addition, all program outputs will be provided as portable document format (PDF) files and will be independently reviewed by a statistician. Upon completion of validation and quality review procedures, all programs and outputs will be retained.

Model assumptions will be checked. If model assumptions are sufficiently violated, then transformations or nonparametric methods of analysis may be used if warranted. Whenever alternative methods of analysis are implemented, the description of the new method along with the rationale for its use will be documented in the CSR. As is customary for contact lens solution trials, eyes will be treated as independent sampling units in eye level analyses unless otherwise noted.

Clinical Data Interchange Standards Consortium (CDISC) standards will be followed to facilitate potential electronic submission. All eCRF data and any externally provided data, such as laboratory data, will be retained in standard data tabulation model (SDTM) datasets. Plus, all data required for the planned analyses, including derived variables, will be provided in analysis data model (ADaM) data sets. The SDTM and ADaM datasets will be provided as SAS® transport files. Data listings will be provided for all relevant collected eCRF and derived data. All Data listings supplied as part of the CSR will be detailed in the relevant sections of this SAP. Each listing be sorted by intervention (first Test, then Control), study center number, subject number, assessment date and/or time point, if applicable.

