#### 4.5.2. Main Analytical Approach

All contrasts and differences will be calculated as Test – Control. All observations will be treated as independent (e.g. each eye and/or each subject).

##### 4.5.2.1. Graded Slit-Lamp Findings > Grade 2

Greater than Grade 2 findings (Absent, Present) overall all follow-up visits will be summarized at the eye level by treatment using categorical summary statistics for the Safety Population. A one-sided upper 97.5% confidence limit around the difference in “Present” proportions between the Test and Control treatment groups will be constructed using the Newcombe-Wilson score method.

If the upper confidence limit is less than 5.0% or if no findings greater than Grade 2 are observed in either treatment group, then the null hypothesis that the Test solution is not noninferior will be rejected, and the Test solution will be statistically successful in this outcome.

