#### 4.5.2.2. Overall Comfort

Mean overall comfort over all follow-up visits will be summarized at the eye level by treatment using continuous summary statistics for the ITT Population. A one-sided lower 97.5% confidence limit around the difference in means between the Test and Control treatment groups, computed using an analysis of variance model including the fixed factors of treatment, site, and lens group will be displayed.

If the lower confidence limit is greater than -5.0, then the null hypothesis that the test solution is not noninferior will be rejected, and the test solution will be statistically successful in this outcome.

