#### 4.5.2.4. Front Surface Deposits

Maximum Front Surface Deposits Over All Follow-up Visits ( $\leq 2$ ,  $> 2$ ) will be summarized at the eye level by treatment using categorical summary statistics for the ITT Population in a table. A one-sided lower 97.5% confidence limit around the difference in " $\leq 2$ " proportions between the Test and Control treatment groups will be constructed using the Newcombe-Wilson score method.

If the lower confidence limit is greater than -10.0% or if no deposits with grade greater than 2 are observed in either treatment group, then the null hypothesis that the Test solution is not noninferior will be rejected, and the Test solution will be statistically successful in this outcome.

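### All four co-primary tests and the power calculation count each subject's two eyes as independent, so any appreciable inter-eye correlation lifts the one-sided error above 2.5%

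*SAP*

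**What the plan says.** The unit of allocation is the subject: "Each subject will be randomized to one of the treatment arms in a 1:1 ratio" (SAP 1.2.2). The unit of analysis is the eye, and "a subject being included in a study population means both of their eyes will be included in the analysis" (SAP 3).

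SAP 4.1 and Protocol 8.6.1.1 state that "eyes will be treated as independent sampling units in eye level analyses unless otherwise noted" and call this customary for contact lens solution trials. SAP 4.5.2 repeats the assumption for the primary analyses. In detail:

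- **Comfort and vision** (SAP 4.5.2.2, 4.5.2.3): the lower limit for the difference in means is "computed using an analysis of variance model including the fixed factors of treatment, site, and lens group will be displayed". There is no subject term.
- **Deposits and slit-lamp findings** (SAP 4.5.2.4, 4.5.2.1): each limit "will be constructed using the Newcombe-Wilson score method", with eyes as the count and no adjustment.
- **Sample size** (Protocol 8.3, SAP 2.2): the outcomes of a subject's two eyes are taken as independent.
- **Level** (SAP 4.1.1, 2.3): every test is one-sided at 0.025, and the overall error is controlled by requiring all four endpoints to succeed.

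**The concern.** The two eyes of a subject share the solution, the care habits and the lens type; an inclusion criterion is "Wears the same brand of contact lens in both eyes" (Protocol 3.3.1.1). The same person gives the 0 to 100 comfort and vision ratings for both eyes (Protocol Appendix B, 7.0). Positive correlation is to be expected, and the documents give no argument that it is zero.

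When both members of a pair are in the same arm, positive correlation makes the analysis believe that it has more information than it has. The confidence limits come out too narrow. In a non-inferiority trial that favours success, and here it affects every test that defines success, including the primary safety test.

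Nothing else in the plan catches this. The per-protocol, best/worst-case and tipping-point analyses (SAP 4.5.3) all repeat the independent-eye method. The model-checking sentence in SAP 4.1 offers only transformations or nonparametric methods, and neither deals with pairing.

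**Working it through.** **Inputs from the documents.** 150 subjects (300 eyes) per arm; one-sided alpha 0.025; SD 13.264 (comfort) and 11.7 (vision), margin -5; deposits proportion 0.942 in both arms, margin -10%; slit-lamp proportion 0.008 in both arms, margin +5% (SAP 2.2.1 to 2.2.4, 4.5.2). **Assumption:** rho, for which no value is given, is taken over 0.1 to 1.0; for the ratings it is the correlation left after site and lens group. The two eyes are exchangeable and both are observed.

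**1. The plan's own figures.** With rho = 0, power is 99.6% for comfort, 99.9% for vision, 99.9% for deposits and 99.9% for slit-lamp. The stated 99% each is reproduced (0.99^4 = 96%). The error at the margin is also near nominal at rho = 0: 2.5% for the ANOVA, 2.5% for deposits and 2.25% for slit-lamp.

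**2. Standard error.** The mean of 300 eyes from 150 subjects has variance sigma^2(1+rho)/300. The plan uses sigma^2/300. The ratio of standard errors is sqrt(1+rho), and the normal approximation to the error at the margin is 1 - Phi(1.96/sqrt(1+rho)).

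**3. Planned ANOVA.** With 22 sites and 5 lens groups the model has 1+1+21+4 = 27 parameters. The eye-level residual has 600 - 27 = 573 degrees of freedom: 300 within subjects with variance sigma^2(1-rho), and 273 between subjects with sigma^2(1+rho). So E(s^2)/sigma^2 = [300(1-rho) + 273(1+rho)]/573, which is 546/573 = 0.953 at rho = 1. The residual variance is too small as well, and the error is 1 - Phi(1.96 x sqrt(0.953/2)) = 8.8% at rho = 1. Simulations of the planned model agree with this closed form to within about 0.3 points; the highest gave 9.1% at rho = 1.

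**4. Proportions.** The distribution of affected eyes was enumerated exactly with P(both eyes) = p^2 + rho p(1-p), at the margin (deposits 0.842 v 0.942; slit-lamp 0.058 v 0.008), and the planned Newcombe-Wilson rule was applied, including its no-events clause.

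| One-sided error at the margin | rho 0.1 | 0.3 | 0.5 | 0.8 | 1.0 |
|---|---|---|---|---|---|
| Normal formula | 3.1% | 4.3% | 5.5% | 7.2% | 8.3% |
| Comfort, vision (planned ANOVA) | 3.1% | 4.4% | 5.7% | 7.6% | 8.8% |
| Deposits | 3.1% | 4.3% | 5.6% | 7.4% | 8.6% |
| Slit-lamp | 2.8% | 3.9% | 5.1% | 7.0% | 7.65% |

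Slit-lamp starts below nominal and reaches 2.5% at rho 0.05.

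**5. Trial level.** Put one endpoint at its margin and the others at their planned values, and multiply its error by the planned-analysis power of the other three. For comfort at rho 0.5 this is about 5.65% x 0.9965 x 0.9935 x 0.9958 = 5.6%. Across the four endpoints the range is about 2.7% to 3.1% at rho 0.1, 5.0% to 5.6% at 0.5, and 7% to 8.5% at 1.0.

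**6. Results that change sides.** The comfort cut-off is -5 + 1.96 x 13.264 x sqrt(2/300) x sqrt(1+rho). For the proportions, n is replaced by 300/(1+rho). Control counts are set near expectation: 300 x 0.008 = 2.4 and 300 x 0.058 = 17.4.

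| Test passes if | as planned | rho 0.1 | 0.3 | 0.5 | 0.8 | 1.0 |
|---|---|---|---|---|---|---|
| Comfort difference above | -2.88 | -2.77 | -2.58 | -2.40 | -2.15 | -2.00 |
| Slit-lamp, 2 Control eyes: Test eyes up to | 9 | 8 | 7 | 7 | 6 | 5 |
| Deposits above grade 2, 17 Control eyes: Test eyes up to | 33 | 32 | 31 | 30 | 28 | 28 |

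For example, 9 v 2 slit-lamp eyes gives an upper limit of 4.98% as planned. At rho 0.8 (effective n 166.7), 6 eyes gives 4.82% and 7 eyes gives 5.29%.

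**7. Power of an analysis that allows for pairing**, with 150 subjects per arm. Comfort and vision use a noncentral t with SD x sqrt((1+rho)/2). The proportions use simulated correlated pairs and a pooled estimate of rho.

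| | rho 0.1 | 0.3 | 0.5 | 0.8 | 1.0 |
|---|---|---|---|---|---|
| Comfort | 99.2% | 98.1% | 96.4% | 92.9% | 90.2% |
| Vision | 99.9% | 99.6% | 98.9% | 97.3% | 95.8% |
| Deposits | 99.7% | 99.1% | 98.1% | 95.6% | 93.4% |
| Slit-lamp | 99.7% | 98.7% | 97.4% | 94.6% | 91.3% |
| Product | about 98% | 96% | 91% | 82% | 74% |

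**The case against.** The choice is open and consistent: both documents state it, design and analysis agree, and it is described as customary. SAP 1 also lets supportive analyses be added without an amendment. That answers any charge of concealment, but it does not restore the 2.5% level, and permission to add a check is not a plan to do one.

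The size rests on an undocumented rho. This stands. The upper figures need rho = 1, where every finding is bilateral and both ratings move together. At rho 0.1 the excess is modest, and for slit-lamp a rho up to about 0.05 does no harm.

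Error at the margin is a worst case. This also stands in part. If the true comfort difference is zero, the planned and adjusted rules disagree on comfort in only about 0.2% of trials at rho 0.1, 2% at 0.5 and 7% at 1.0. At rho 0.3 the adjusted overall power is still about the stated 96%. But a non-inferiority level is defined at the margin, and requiring all four to pass gives no protection when three are comfortable and one is not.

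The remedy is weaker for slit-lamp. About 0.008 x 600 = 4.8 affected eyes are expected in all, so an estimated rho is unstable. The practical harm is limited: with 4 or fewer affected eyes in total, the upper limit is below 5% even at rho = 1 (4 v 0 gives 4.73%), so Test passes whatever rho is.

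**Conclusion.** The concern holds. As written, the four primary tests do not have the stated one-sided 2.5% level unless the two eyes are uncorrelated or very nearly so. For an assumed rho of 0.1 to 1.0, the error at the margin is about 3% to 9% for comfort, vision and deposits and 2.8% to 7.65% for slit-lamp findings. The trial-level error is close to this when one endpoint sits at its margin. The stated power is likewise that of an analysis with rho = 0.

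The direction follows from randomising subjects and analysing eyes. The size depends on rho, which the sponsor may be able to estimate from the earlier study that supplied the SDs and proportions (Protocol 8.3). The slit-lamp range also depends on the planned Control rate of 0.008.

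**What to change.** Amend SAP 4.1 and 4.5.2 and Protocol 8.6.1 so that the primary analyses respect the subject as the unit; if only the SAP is changed, record it in SAP 4.10.

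- **Comfort and vision:** keep treatment, site and lens group, and analyse the mean of the subject's two eyes, or add a subject random effect. In simulation the subject-mean ANOVA held 2.4% to 2.6% over the whole range of rho. Little is lost to one-eyed data, because the mandatory reasons for discontinuing a subject include "Either eye is discontinued" (Protocol 3.3.3).
- **Deposits and slit-lamp findings:** prespecify a cluster-adjusted interval for the difference in eye proportions. One option is Newcombe-Wilson limits with effective size n/(1+rho-hat), with rho-hat pooled over arms. In simulation this gave 2.4% to 2.6% for deposits and 1.7% to 2.4% for slit-lamp, so it is somewhat conservative for the latter. Add a prespecified rule for sparse events, with operating characteristics checked by simulation by the sponsor's statistician. The no-events success rule can stay.
- **Reporting:** keep the independent-eye result as supplementary. Restate per-endpoint and overall power in SAP 2.2 and Protocol 8.3 for a stated range of rho.

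The cost is wording and code, with no new data. The trade-off is real: limits widen by sqrt(1+rho), which is 5% at rho 0.1, 14% at 0.3, 22% at 0.5, 34% at 0.8 and 41% at 1.0. The sponsor must accept the lower power shown above or enrol more subjects.

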#### 4.1.1. Common Statistical Methods and Data Presentations

Unless otherwise specified, safety analyses will be based on the Safety Population and efficacy analyses will be based on the ITT Population or the PP Population (sensitivity analyses of primary efficacy analyses only). Other non-safety analyses (i.e. demographic information) will use the ITT Population (unless noted otherwise). Summaries will include results for each intervention separately. Some summaries will also include results for all subjects regardless of intervention (i.e. demographics and baseline characteristics).

All statistical tests will be 1-sided with a nominal alpha of 0.025 (2.5%). Endpoints relating to the Subject Assessment Questionnaire will include multiplicity adjustment of the p-value via a hierarchical two-family Holm procedure: type 1 error will remain at 0.025. Otherwise, there will be no adjustment for multiplicity.

The respective sections of this SAP will detail the statistical analyses, including use of the stratification variables (consisting of (1) lens group and (2) investigational site).

Categorical data will be presented using the total counts for each category and corresponding percentages. The denominator for each percentage will be the number of subjects or eyes with non-missing data unless otherwise indicated. Presentation will be of the form XXX (XX.X %), where the percentage is reported to one decimal place in parentheses. In the case of a frequency

of zero, the frequency and percentage will be presented as 0 rather than 0 (0%). Any single-arm confidence intervals on the proportion will be performed by exact methods, unless stated otherwise.

Summaries for continuous variables will include the number of subjects (or eyes) in the analysis, mean, standard deviation, median, minimum, and maximum. All mean and median values will be formatted to one more decimal place than the measured value. Standard deviation values will be formatted to two more decimal places than the measured value. Minimum and maximum values will be presented with the same number of decimal places as the measured value.

Date variables will be formatted as DDMMYY for presentation.

#### **4.1.2. Missing Data, and Data Errors**

For non-Safety Population analyses, subjects who receive a study intervention other than the one to which they were randomized will be presented according to their randomized intervention. Safety analyses will use the intervention actually dispensed: if a subject is ever given Test (even if they were initially dispensed Control), they will be treated as actually receiving Test for safety analyses. Data listings will clearly denote whether randomized or actual intervention is being used. These subjects will be noted in the CSR. Likewise, any other data errors identified in the final database will simply be noted in the CSR so long as the error does not impact the findings of the study.

The effect of missing data on the primary effectiveness endpoint analyses will be explored by considering best- and worst-case imputation scenarios and tipping point analysis with the ITT Set, which will be further described in this SAP.

Otherwise only observed data will be used for the study objective. All data summaries will identify the number of subjects (or eyes) with data, so the number of subjects (or eyes) with missing data for each variable can be deduced from the data summaries.

Handling of other types of missing data, e.g., missing attributes of an adverse event (AE), like start date or relatedness, will be addressed in the respective sections of this SAP.

#### **4.1.3. Coding of Concomitant Medications and Adverse Events**

Adverse events (AE) and medical/ocular history will be coded using the Medical Dictionary for Regulatory Activities (MedDRA™), and concomitant medications will be coded using the World Health Organization Drug Dictionary (WHODD). The versions of the dictionaries used for reporting are specified in the Data Management Plan (DMP) and will be reported in the CSR.

